## **5.4     *Subject Compliance Monitoring***

All subjects are expected to receive study therapy as outlined in the protocol. Subjects will use diary cards to document self-injection of study drug between clinic visits.

## **5.5     *Prior and Concomitant Therapy***

Patients with newly diagnosed or established seropositive active RA will be allowed to enter this clinical trial that meet the above inclusion and exclusion criteria. The

ideal candidate for this trial is newly diagnosed RA about to be initiated on weekly methotrexate therapy (20 mg/week or the maximally tolerated dose). Prior or concurrent therapy with methotrexate or hydroxychloroquine ( $\leq$  400 mg/d). Established treatment (>4 weeks) with daily Prednisone ( $<10$  mg/d) is permitted.

## **5.6 Packaging**

N/A

## **5.7 Blinding of Study Drug**

N/A

## **5.8 Receiving, Storage, Dispensing and Return**

### **5.8.1 Receipt of Drug Supplies**

Upon receipt of the of the study treatment supplies, an inventory must be performed and a drug receipt log filled out and signed by the person accepting the shipment. It is important that the designated study staff counts and verifies that the shipment contains all the items noted in the shipment inventory. Any damaged or unusable study drug in a given shipment (active drug or comparator) will be documented in the study files. The investigator must notify study sponsor of any damaged or unusable study treatments that were supplied to the investigator's site.

### **5.8.2 Storage**

The fully diluted Abatacept solution may be stored at room temperature or refrigerated at 36°F to 46°F (2°C to 8°C) before use. The infusion of the fully diluted Abatacept solution must be completed within 24 hours of reconstitution of the Abatacept vials. Discard the fully diluted solution if not administered within 24 hours.

The infusion of the fully diluted Abatacept solution must be completed within 24 hours of reconstitution of the Abatacept vials. Discard the fully diluted solution if not administered within 24 hours.

### **5.8.3 Dispensing of Study Drug**

The investigator is responsible for ensuring adequate accountability of all used and unused study drugs. This includes acknowledgement of receipt of each shipment of study drugs (quantity and condition). All used and unused study drugs dispensed to subjects must be returned to the site.

Abatacept accountability records will be provided by Dartmouth-Hitchcock Investigational Pharmacy:

- Record the date received and quantity of study drugs

- Record the date, subject number, subject initials, the study drug number dispensed
- Record the date, quantity of used and unused study drugs returned, along with the initials of the person recording the information.
- Dispensing records will include the initials of the person dispensing the study drug

#### **5.8.4 Supplies, Return or Destruction of Study Drug**

At the completion of the study, there will be a final reconciliation of drug shipped, drug consumed, and drug remaining. This reconciliation will be logged on the drug reconciliation form, signed and dated. Any discrepancies noted will be investigated, resolved, and documented prior to return or destruction of unused study drug. Drug destroyed on site will be documented in the study files.

For this study, study drugs (those supplied by BMS or sourced by the investigator) such as partially used study drug containers, vials and syringes may be destroyed on site. Any unused study drugs can only be destroyed,

#### **5.9 *Vi sit 1***

See above

#### **5.10 *Visit 2***

#### **5.11 *etc.***

### **6 Statistical Plan**

#### **6.1 *Sample Size Determination***

Not applicable, this is a pilot study

#### **6.2 *Statistical Methods***

These studies are considered exploratory and will enable power analyses for subsequent larger studies. We anticipate that clinical responders will concurrently have more than 25% decreases in IgG anti-CCP3 levels (ANOVA). The mean change in IgG anti-CCP levels in responders versus non-responders will be analyzed by t-test. A proportional decrease in the estimated level of IgG anti-CCP3 secreting recirculating memory B cells is predicted as well. Clinical non-responders are predicted to not have a significant change. No significant effects on total IgG, IgA or IgM are anticipated. In a recent report with cross-sectional analyses we documented highly significant correlations  $r=0.57$   $p=0.0033$  between ACPA and memory B cell levels in studies of 24 RA patients (11). With longitudinal analyses we anticipate that relationships should require fewer subjects to document correlations between shifts in clinical activity and ACPA IgG and ACPA-memory B cell levels overtime. We will

assess non-parametric paired-sample comparisons by Spearman correlations, and longitudinal measurements using paired t test, with Prism v6.0e (GraphPad, La Jolla, CA). P<0.05 will be considered significant.

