### 3 Study Design

#### 3.1 General Design

A phase IV open-label clinical trial in which each CCP/ACPA+ patient will be their own longitudinal control for the immunomodulatory activity of Abatacept. All patients will have blood collection, including for peripheral blood mononuclear cells (PBMC), PBMC RNA and plasma, at screening and at day 0 after which Abatacept will be initiated in concert with methotrexate or pre-existing csDMARD. Each patient will then be reevaluated at 3 months and 6 months. In all patients, Abatacept will be discontinued after 6 months. Patients who have flared or failed to achieve low disease activity at 6 months, will exit the trial except for one post study visit for lab work at 9 months.

In patients who have achieved low disease activity by DAS28-CRP (<3.2) or CDAI (<10), Abatacept will be held for 6 months or until a flare results. A flare is defined by an examination demonstrating a DAS28-CRP that is greater than an absolute value of 4.0) or a CDAI >15, both defining the mid-range of a moderate flare. Alternatively, a 30% increase in the absolute level of the DAS28-CRP or CDAI that result in measures of 3.2 and 10 respectively, will be considered evidence of a flare. If patients do not experience a flare after 6 months off Abatacept (by week 52) they will also exit the study after a final visit with an exit blood draw.

Overall, in this pilot study, patient screening will continue until 25 suitable patients are enrolled and started on therapy in the trial. We predict enrollment of 2-3 patients/month, and hence the study should be fully enrolled by month 14 with the expectation that 70-80% will achieve low disease activity at week 24 enabling 17-20

patients to be followed for flare following Abatacept dechallenge. This estimate is based on the observation that treat provides nearly 60% ACR 50 responses, despite the fact that patients were selected for evidence of erosive disease.

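### Section 6.2 names Spearman correlation as its non-parametric paired comparison and attaches an unspecified ANOVA to a fall of more than 25%; neither, as named, answers the question it is attached to

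*Combined protocol and SAP*

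**What the plan says.** Section 6.2 (Statistical Methods) is the only statistical methods text in the document. It makes these statements on the antibody and B-cell measures.

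- Prediction for responders: "We anticipate that clinical responders will concurrently have more than 25% decreases in IgG anti-CCP3 levels (ANOVA"). The bracket holds only the name of the method. No factors, time points, contrast, null value or confidence interval are given.
- Responders against non-responders: "The mean change in IgG anti-CCP levels in responders versus non-responders will be analyzed by t-test".
- Paired and repeated data: the plan will "assess non-parametric paired-sample comparisons by Spearman correlations, and longitudinal measurements using paired t test".
- Significance: "P<0.05 will be considered significant". Sidedness is not stated.
- Status: "These studies are considered exploratory and will enable power analyses for subsequent larger studies".

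Section 6.1 gives no sample size calculation: "Not applicable, this is a pilot study". Section 3.1 sets a single group of 25 and plans on this basis: "with the expectation that 70-80% will achieve low disease activity at week 24 enabling 17-20" patients to be followed after abatacept is stopped. Sections 2 (Primary Objective) and 3.2 make the relation between clinical response and the B-cell and antibody measures a co-primary matter.

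**The concern.** Two methods are paired with questions that they do not answer.

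**Spearman.** A paired comparison asks whether levels moved between two samples from the same patient. Spearman asks whether patients keep their rank order. For a stable marker, baseline and follow-up values correlate strongly whether or not the level changed. An analyst who took the non-parametric route literally would get a small P value that says nothing about change.

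**ANOVA.** The sentence contains a threshold, but the method beside it has no threshold in its usual null hypothesis. A significant result would be compatible with a mean fall well short of 25%.

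At stake is how a co-primary mechanistic question is read. There is also a practical loss: the stated purpose is to support power analyses for later studies, and those need an estimated change with its spread. Neither a bare ANOVA P value nor a rank correlation between two time points supplies that.

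**Working it through.** The plan contains no design calculation to reproduce. The check is of what each named method tests, followed by the size of the gap.

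**1. Spearman on paired levels.** Let x be the baseline value, y the follow-up value and c a positive constant. Then rank(c·y) = rank(y), so rho(x, c·y) = rho(x, y). This needs no assumption about the data. As an illustration, one set of 20 pairs was simulated (assumed baseline log SD 1.0, log SD of change 0.3) and the follow-up values were multiplied by c:

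| c | Spearman rho | Spearman P | Wilcoxon signed-rank P |
|---|---|---|---|
| 1 | 0.83 | 0.000006 | 0.29 |
| 0.75 | 0.83 | 0.000006 | 0.00004 |
| 0.4 | 0.83 | 0.000006 | 0.000002 |
| 0.1 | 0.83 | 0.000006 | 0.000002 |

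Over 1,500 simulated trials with n = 25 (assumed log SD 1.0 between patients and 0.25 within), Spearman had mean rho 0.92 and P<0.05 in 100% of trials, both with no change and with every value halved. Wilcoxon signed-rank rejected in about 5% and 100% respectively.

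**2. What an ANOVA tests.** With two time points, the repeated-measures F is the square of the paired t, and the null is a mean change of zero. With two groups, F is the square of the two-sample t, and the null is no difference between groups. In a simulated 18-against-7 example, t = -2.371 and F = 5.621 = t², with the same P of 0.0265. With more time points the null is that all means are equal. A 25% limit appears in none of these.

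**3. Size of the gap.** Inputs:

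- n = 17 and n = 20 responders, from section 3.1 (0.70 × 25 = 17.5 and 0.80 × 25 = 20).
- Two-sided 0.05, the level from section 6.2 and the sidedness assumed.
- SD of the log ratio of follow-up to baseline: 0.2 to 0.5. This is an assumption; the documents give no figure.

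Half-width of the 95% CI on the log scale: h = t(0.975, n-1) × SD / √n.
Smallest observed fall significant against no change: 1 - exp(-h).
Smallest observed fall whose whole 95% CI lies beyond 25%: 1 - 0.75 × exp(-h).

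- n = 20, SD 0.2: h = 2.093 × 0.2 / 4.472 = 0.0936. The falls are 8.9% and 31.7%.
- n = 17, SD 0.5: h = 2.120 × 0.5 / 4.123 = 0.2571. The falls are 22.7% and 42.0%.

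So, across the assumed range, significance against no change begins at an observed fall of about 9% to 23%. The data would exclude 25% or less only from about 32% to 42%.

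**4. If the true fall is 15%.** Share of trials with P<0.05 in a test of no change (20,000 simulated trials per cell; the noncentral t agrees to within one percentage point):

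| n | SD 0.2 | SD 0.3 | SD 0.4 | SD 0.5 |
|---|---|---|---|---|
| 17 | 88% | 55% | 35% | 24% |
| 20 | 93% | 63% | 41% | 28% |

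A one-sided 0.025 test against the 25% limit is significant in 0.2% of these trials or fewer.

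**The case against.** The case on the other side has four parts.

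- **Change is covered by another test.** The same sentence of 6.2 gives longitudinal measurements to the paired t test, and before-and-after levels are longitudinal. This stands. A reader might infer from the Spearman clause that the plan has no means of detecting a treatment effect; the documents do not support that. What remains is that the clause labelled non-parametric and paired names no method that compares levels.
- **Spearman may be meant for association.** The preceding sentence of 6.2 concerns correlations between shifts in clinical activity and in antibody and B-cell levels, and sections 2 and 3.3 have the same aim. Spearman suits that. The plan does not say that it will correlate baseline with follow-up values of one marker, so the simulations in step 1 show what the literal label would give, not what the sponsor has said it will do. If association was meant, the wording should say so.
- **The 25% figure is a prediction.** It is introduced as an expectation, in a pilot described as exploratory. A reader might infer that a significant ANOVA is to be reported as confirming a fall above 25%; no sentence says so. This stands and lowers the weight.
- **The ANOVA is unspecified.** A model with a contrast against a 25% reduction could address the prediction. None is given, so the fair criticism is that the method as named does not do so, not that no ANOVA could.

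The magnitudes also depend on an assumed SD, which is why a wide range is shown.

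**Conclusion.** The point holds, with moderate weight. Section 6.2 names no valid non-parametric paired test, because Spearman cannot act as one. That conclusion is mathematical and needs no assumption. The section also places an unspecified ANOVA beside a 25% prediction that an ordinary ANOVA does not test. How far the two can diverge depends on the assumed SD of 0.2 to 0.5 and on 17 to 20 responders; the mismatch between test and threshold does not.

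It is not a fatal fault. Data collection and the clinical endpoint are untouched, the paired t test covers within-patient change parametrically, and no decision hangs on the 25% figure.

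**What to change.** Revise section 6.2 before analysis.

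1. Name the Wilcoxon signed-rank test for non-parametric paired comparisons. Keep Spearman for associations between different variables or between their changes, and say so.
2. For IgG anti-CCP3 in responders, report the geometric mean ratio of Month 6 to day 0 with its 95% CI, and interpret the 25% prediction against that interval. A pass-or-fail rule on the upper limit is not needed in an exploratory pilot.
3. If the ANOVA stays, state its factors, time points and contrast, and state that a significant result will not be cited as evidence of a fall above 25%.

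The cost is wording only: no added patients, visits or samples. The downside is that the 25% statement becomes harder to support, since an interval lying wholly beyond 25% would need an observed fall of roughly 32% to 42% under the assumed SDs. In return, the ratio and its interval give later studies the effect size and spread that this pilot is meant to provide.

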## **2 Study Objectives**

As a step toward a cure, we will directly assess the impact of a treatment on the underlying autoimmune disease process. Because Abatacept has unique mechanisms of action we believe that ABATACEPT treatment ameliorates RA clinical disease activity through beneficial effects on the pathologic breaches in adaptive immunity that are causal for disease. We will therefore conduct a prospective open therapeutic trial with adult seropositive (i.e., ACPA-positive) RA patients and perform intensive quantitative surveys of pathologic autoantigen-specific B cell memory.

We will test whether the clinical benefit induced by ABATACEPT treatment are paralleled by reductions (i.e., normalization) in the in vivo representation of disease-associated anti-citrullinated protein antigen (ACPA) memory B cells after 6 months of treatment. The corollary is to determine whether reductions of disease-associated memory B cells are the most meaningful marker of therapeutic response? ii) Hypothesis 2: The cessation of ABATACEPT treatment (i.e., dechallenge) with continued methotrexate therapy results in clinical flare, is then paralleled by reaccumulation in the bloodstream of disease-associated ACPA memory B cells.

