### 3.2 Primary Study Endpoints

To assess the efficacy of Abatacept + csDMARD to induce low disease activity [DAS28-CRP (<3.2) or CDAI (<10) that can be maintained on csDMARD alone. A necessary co-primary objective is the relationship between clinical response and changes in B cell and antibody parameters that are unaffected by TNF-inhibition.

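### Section 6.2 tests the antibody link with a responder t-test that is not baseline-adjusted and names no main co-primary analysis; a baseline-adjusted continuous model would be more sensitive.

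*Combined protocol and SAP*

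**What the plan says.** The question is set in two places. Section 3.2 states: "A necessary co-primary objective is the relationship between clinical response and changes in B cell and antibody parameters that are unaffected by TNF-inhibition". Section 2 frames the same idea as a parallel between two changes: "We will test whether the clinical benefit induced by ABATACEPT treatment are paralleled by reductions" in ACPA memory B cells after 6 months of treatment.

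Section 6.2 offers several tools for it:

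- A two-sample test: "The mean change in IgG anti-CCP levels in responders versus non-responders will be analyzed by t-test".
- An ANOVA, attached to an anticipated fall of more than 25% in anti-CCP3 among responders. Its factors are not given.
- An expectation that longitudinal data will show "correlations between shifts in clinical activity and ACPA IgG and ACPA-memory B cell levels overtime".
- A closing sentence on methods: the investigators will "assess non-parametric paired-sample comparisons by Spearman correlations, and longitudinal measurements using paired t test", and "P<0.05 will be considered significant".

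The section does not define responder, does not say whether change is absolute, percentage or log, and does not name one of these as the main co-primary analysis. No baseline titre covariate appears anywhere. The likely group sizes follow from section 3.1, which enrols 25 patients "with the expectation that 70-80% will achieve low disease activity at week 24".

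**The concern.** The objective asks whether more clinical benefit goes with a larger fall in antibody. DAS28-CRP, CDAI and blood samples are all scheduled at Day 1 and Month 6, so both sides of that relationship are available as continuous changes. The t-test reduces the clinical side to two unequal groups and compares unadjusted changes between groups that were not randomised.

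Three things are at stake:

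- **Sensitivity.** A contrast against 5-8 non-responders is imprecise.
- **Interpretation.** If responder is an attained state, it need not track improvement. Entry requires at least moderate activity (CDAI above 16). A patient going from CDAI 17 to 9 falls by 47% and is a responder. One going from 45 to 12 falls by 73% and is a non-responder, provided DAS28-CRP is also 3.2 or more, since either index can qualify.
- **Baseline.** Responders and non-responders may start at different titres. If falls are roughly proportional, absolute change depends on the starting titre, and section 6.2 leaves the scale open.

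**Working it through.** **Inputs.** From the documents: N = 25 and 70-80% reaching low disease activity (section 3.1); significance level 0.05 (section 6.2; taken as two-sided, which is not stated); r = 0.57 in 24 patients (section 6.2). Assumed: responder means low disease activity at Month 6; normal distributions; baseline-to-follow-up correlation ρ of 0.7-0.9; partial correlation between clinical change and follow-up titre of 0.4-0.57. The upper value borrows the protocol's r only as a benchmark, because that figure relates ACPA to memory B cells cross-sectionally.

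**1. The plan's own figures.** 25 × 0.70 = 17.5 and 25 × 0.80 = 20, which matches the stated 17-20 and leaves 5-8 non-responders. For r = 0.57 and n = 24, t = 0.57 × √22 / √(1 − 0.57²) = 3.25, two-sided p = 0.0036. This agrees with the printed 0.0033 within rounding of r (0.575 gives 0.0033).

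**2. Information kept by the split.** Cutting a normal variable at proportion p keeps φ(z)² / [p(1 − p)].

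- p = 0.70: z = 0.524, φ = 0.348; 0.348² / 0.21 = 0.58.
- p = 0.80: z = 0.842, φ = 0.280; 0.280² / 0.16 = 0.49.

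The loss is therefore 42-51%.

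**3. What the t-test can detect.** For 80% power it needs a standardised difference of 1.25 (17 versus 8) to 1.46 (20 versus 5). At a difference of 1.0 its power is 61% and 48% respectively.

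**4. Baseline.** The residual variance with a baseline covariate, relative to a change score, is (1 − ρ²) / [2(1 − ρ)] = (1 + ρ)/2. That is 0.85 at ρ = 0.7 and 0.95 at ρ = 0.9, a saving of 15% down to 5%.

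**5. Power by simulation.** n = 25, 20,000 trials per cell, ρ = 0.7, 0.8 or 0.9, responder share 70% or 80%. Clinical change is independent of baseline titre. The responder group is a cut of continuous clinical change. With no true relation, every method rejects in 4.6-5.6% of trials. Entries are ranges over ρ and responder share.

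| Partial r | t-test on change | Spearman on change | Regression with baseline |
|---|---|---|---|
| 0.40 | 24-30% | 40-46% | 50-51% |
| 0.50 | 35-46% | 60-66% | 72-73% |
| 0.57 | 45-59% | 74-80% | 86% |

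Cell by cell, regression gains 20-41 points over the t-test and 6-13 over Spearman. Repeat runs of the same model stretch these slightly, so I quote about 20-43 and 5-14.

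**6. How much Spearman already recovers.** At r = 0.5, ρ = 0.7, 70% responders: (59.9 − 41.5) / (73.2 − 41.5) = 58%. At r = 0.57, ρ = 0.9, 80% responders: (79.2 − 49.8) / (85.8 − 49.8) = 82%. These are the lowest and highest cells.

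**The case against.** The strongest reply is that section 6.2 already contains a continuous analysis. It anticipates correlations between clinical shifts and ACPA IgG and names Spearman. That stands. A reader might infer from the t-test that the plan as a whole throws away half the clinical information and can miss the co-primary link. The documents do not support this: the 42-51% loss belongs to the t-test alone, and the fair comparison for the whole plan is with Spearman. What remains is that the Spearman sentence gives no variables, visit or scale, is not given priority, and carries no baseline adjustment.

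Other replies also have force:

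- The t-test cannot be called the only between-group antibody test, because the ANOVA is also attached to responders. It is the only one whose outcome and groups are both stated.
- It would be wrong to say baseline is ignored. A change score subtracts it, and the 25% prediction is relative to it. What is missing is a covariate and a fixed scale.
- In non-randomised groups, covariate adjustment is not automatically less biased than a change score. The two answer different questions, which is a reason to choose one in advance.
- The power figures model a cut of clinical change. They do not measure the cost of using an attained state.
- This is a 25-patient pilot, labelled exploratory, with no sample size calculation. That lowers the weight of any power loss. However, section 6.2 also says the results will feed later power analyses, and a slope with its residual variance serves that purpose better than a contrast with 5-8 patients.

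**Conclusion.** The point holds in a limited form. The responder t-test is an inefficient, baseline-unadjusted way to examine the co-primary relationship, keeping 49-58% of the information in a continuous clinical change. Section 6.2 does not say that any better analysis takes precedence over it. Against the whole plan, including Spearman on change, the realistic gain from a baseline-adjusted continuous model is about 5-14 power points; the 20-43 points apply only against the t-test.

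These sizes rest on normality, a responder cut at Month 6 low disease activity, a partial correlation of 0.4-0.57 and a baseline-to-follow-up correlation of 0.7-0.9. The documents supply neither correlation. The part due to baseline adjustment shrinks as the second correlation rises. This is a worthwhile improvement to an exploratory plan and does not invalidate it.

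**What to change.** In section 6.2:

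1. Name as the main co-primary analysis a linear model of log IgG anti-CCP3 at Month 6 on log baseline anti-CCP3 and the continuous Day 1 to Month 6 change in CDAI. Use DAS28-CRP change as a sensitivity analysis.
2. Apply the same model to ACPA memory B cells.
3. Keep Spearman as the rank-based check, stating that it correlates Day 1 to Month 6 changes and on which scale.
4. Keep the responder/non-responder contrast as a supportive description, with responder defined and the scale of change fixed.

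The cost is SAP wording; the schedules of events already collect the assessments and blood samples at both visits. There are two small downsides. The model assumes an approximately linear relation on the log scale, with Spearman as the safeguard. Its coefficient is an association conditional on baseline, not the difference in mean change, and should be reported as such because response is not randomised.

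### Section 6.2 states no responder v non-responder test of change for ACPA memory B cells, so its forecast of no significant change would rest on 5-8 non-responders; report between-group differences with 95% CIs

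*Combined protocol and SAP*

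**What the plan says.** Section 6.2 anticipates that clinical responders will show falls of more than 25% in IgG anti-CCP3, with ANOVA given in brackets and not described further. For the antibody it plans a direct comparison: "The mean change in IgG anti-CCP levels in responders versus non-responders will be analyzed by t-test". For the cells it says "A proportional decrease in the estimated level of IgG anti-CCP3 secreting recirculating memory B cells is predicted as well" (taken here as the ACPA memory B-cell measure of the objectives). For the other group it says "Clinical non-responders are predicted to not have a significant change".

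The remaining methods are Spearman correlations, including "correlations between shifts in clinical activity and ACPA IgG and ACPA-memory B cell levels overtime", and "longitudinal measurements using paired t test", with no biomarker or patient group named for the paired test. The criterion is "P<0.05 will be considered significant". No confidence intervals are mentioned.

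Section 6.2 does not define a non-responder. Section 3.1 separates patients by low disease activity at 6 months, and its schedules of events carry matching titles, so that reading is used here. Section 3.1 gives "the expectation that 70-80% will achieve low disease activity at week 24 enabling 17-20" patients for the follow-up after abatacept is stopped. Section 6.1 gives no sample size because the study is a pilot.

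**The concern.** A non-significant change in a handful of patients is not evidence that nothing changed. Nor is a significant change in one group beside a non-significant change in the other evidence that the groups differ. With 17-20 responders and 5-8 non-responders, that pattern can arise from group size alone, and the fewer the non-responders, the more easily the forecast appears to be confirmed.

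This bears on the co-primary objective in section 3.2, which is the relationship between clinical response and change in B-cell and antibody parameters. For IgG anti-CCP the planned t-test addresses it directly. For memory B cells, which are central to the study hypothesis, no such test is stated. A reader has the correlation or the within-group contrast that the forecast invites. Section 6.2 also says the study "will enable power analyses for subsequent larger studies". That purpose needs estimates and their precision, which a within-group P value does not supply.

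**Working it through.** **Group sizes.** From section 3.1: 25 × 0.70 = 17.5 and 25 × 0.80 = 20, which reproduces the stated 17-20. Non-responders: 25 − 20 = 5 and 25 − 17 = 8.

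**Other inputs.** Alpha is 0.05 (section 6.2), taken as two-sided because sidedness is not stated. The true fall is set at 25 percentage points in both groups. That figure is borrowed from the responder forecast for IgG anti-CCP3; for memory B cells 6.2 gives no number, so there it is an assumption. The documents give no SD of change, so 15, 20, 30 and 40 points are assumed. Changes are taken as normal with equal SD, and all 25 patients as having month-6 data.

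**Within-group tests.** Power of the paired t-test is the probability that a noncentral t with n − 1 df and noncentrality (25/SD) × √n exceeds the two-sided critical value. Example at SD 30 and n = 5: noncentrality 0.833 × 2.236 = 1.86, critical value 2.776, power 0.300, so the fall is missed with probability 0.700. With n = 20: noncentrality 0.833 × 4.472 = 3.73, power 0.942.

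**The misleading pattern.** The groups are independent, so P(responders significant, non-responders not) = responder power × non-responder miss probability. At SD 30 with 20 v 5: 0.942 × 0.700 = 0.66.

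| SD (points) | Miss, n=5 / n=8 | Responder power, n=20 / n=17 | Pattern under equal change, 20 v 5 / 17 v 8 |
|---|---|---|---|
| 15 | 0.207 / 0.020 | about 1 / about 1 | 0.21 / 0.02 |
| 20 | 0.438 / 0.144 | >0.999 / 0.998 | 0.44 / 0.14 |
| 30 | 0.700 / 0.472 | 0.942 / 0.897 | 0.66 / 0.42 |
| 40 | 0.808 / 0.667 | 0.755 / 0.677 | 0.61 / 0.45 |

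The rate levels off at SD 40 because the responder test also loses power.

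**What a direct test adds.** With equal true change, a between-group t-test is significant in 5% of trials by construction. In 40,000 simulated trials per setting (SD 20 to 40), the pattern came together with a significant between-group test in only about 2-3%.

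**Precision of the estimates.** The 95% CI half-width is t × SD/√n for one group: 2.776/√5 = 1.24 SD at n = 5, and 2.365/√8 = 0.84 SD at n = 8. For the difference it is t × SD × √(1/a + 1/b) with 23 df: 2.069 × √(1/20 + 1/5) = 1.03 SD, and 2.069 × √(1/17 + 1/8) = 0.89 SD. In points:

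| SD | Non-responder change, n=5 / n=8 | Difference, 20 v 5 / 17 v 8 |
|---|---|---|
| 15 | 18.6 / 12.5 | 15.5 / 13.3 |
| 20 | 24.8 / 16.7 | 20.7 / 17.7 |
| 30 | 37.2 / 25.1 | 31.0 / 26.6 |
| 40 | 49.7 / 33.4 | 41.4 / 35.5 |

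Power of the between-group t-test for a true 25-point difference (20 v 5 / 17 v 8) is 89/96% at SD 15, 67/80% at SD 20, 36/46% at SD 30 and 22/29% at SD 40. A non-significant difference would therefore not settle the question either, which is why the interval should be reported.

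**The case against.** The sentence is a forecast. Section 6.2 nowhere says that a non-significant result in non-responders will be taken as no change, and it does not name non-responders as a group for the paired test. A reader might infer a decision rule from it; the text does not contain one. This stands, and it limits the point.

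A reader might also infer that the plan has no valid comparison of the two groups. That is wrong for IgG anti-CCP, where the t-test is stated. The bracketed ANOVA is attached to the IgG anti-CCP3 prediction and is not specified, so it cannot be counted either as covering memory B cells or as irrelevant.

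A third inference is that the co-primary has no deciding analysis and that this is a separate defect. The documents do not support that. The Primary Objective in section 2 calls for correlations with clinical response measures, and the Secondary Objective and section 3.3 say the co-primary endpoints will be correlated over time and the relationship then confirmed after abatacept is stopped. Together with the correlations in 6.2, this leans towards correlation. In a declared exploratory pilot, the lack of a formally ranked lead analysis is missing detail and not an error.

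Finally, the size depends on an SD that the documents do not give. At SD 15 with 8 non-responders the misleading pattern is rare (2%). That also stands, which is why the range is shown from 15 upwards. What remains at any SD is that non-significance does not show absence of change.

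**Conclusion.** The point holds for the memory B-cell measure, at minor severity. Section 6.2 states no responder v non-responder test of its change, so the forecast contrast could be judged only from significance within groups, one of which is expected to have 5-8 patients. With an equal true fall of 25 points, that reading would mislead in about 2-21% of trials at SD 15, 14-44% at SD 20, 42-66% at SD 30 and 45-61% at SD 40 (the two ends of each range being the 17 v 8 and 20 v 5 splits). For IgG anti-CCP the planned t-test already gives the valid comparison; what is missing there is an estimate with its interval.

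The figures rest on the assumed SDs, the borrowed 25-point fall, two-sided tests, and non-responder meaning not in low disease activity at month 6. They also assume complete month-6 data. Section 4.4.2 treats later data of withdrawn or lost patients as missing, so the groups may be smaller and the estimates less precise.

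**What to change.** In section 6.2, replace the forecast of no significant change with the following:

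1. For IgG anti-CCP and for ACPA memory B cells, report the mean change from baseline to month 6 in responders, the same in non-responders, and the between-group difference, each with a 95% CI and the number of patients with data.
2. State that whether biomarker change tracks clinical response will be judged from that difference and from the correlation already planned, and not from significance or non-significance within either group.
3. Define responder and non-responder for this analysis, and state how the ANOVA fits with the t-test and the correlations.

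The cost is wording only: no added patients, visits or assays. The downside is that the non-responder result will be shown openly as imprecise, with the wide intervals given in the working.
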